The primary outcome of the trial will be quality of PrEP counseling, summarized by an SP checklist score at unannounced clinic visits that will assess communication (e.g. listening without interruption, encouraged questions) and adherence to national guidelines on PrEP counseling and delivery (e.g. risk assessment, counseling on key messages, correct medication recommended). The secondary outcome, assessed in intervention arm will be change in interpersonal skills mean score percent between the first and last session. Communications and interpersonal skills measures are adapted from the Kalamazoo Consensus Statement (31) and other published tools (32-34)

SAMPLE SIZE CONSIDERATIONS

Primary trial outcome: Given a fixed number of clusters (24 facilities), we estimated the minimum number of SP encounters required to detect a 20 percentage-point difference in PrEP counselor competency score between intervention and control arms. Because it is uncertain what baseline PrEP competency will be, we estimated sample sizes to detect a 10-percentage point difference between the intervention and control arm varying the baseline competency percent, shown in Table 2. Under these assumptions, if PrEP competency is 61% in the control arm using baseline data and standard deviation of 17.7%, we would need an estimated 112 to 120 total SP encounters (4 to 6 per site). We will plan to conduct 6 visits per site (120 total), which assumes we only have 20 facilities, to ensure we have adequate power. Higher baseline competency would require a larger sample size to detect the same difference. The expected upper limit of SP encounters is 400.

Table 1. Sample sizes of SP encounters to detect a 10-percentage point difference in competency at 80% power, correlation coefficient (k) of 0.15, $\alpha=0.05$ and 24 facilities

Control group competency %	Intervention group competency %	Minimum cluster per arm required	SP encounters per cluster	Total SP encounters
0.61	0.71	14	4	112
0.61	0.71	11	5	110
0.61	0.71	10	6	120
0.61	0.71	8	7	112
0.61	0.71	8	8	128
0.61	0.71	7	9	126
0.61	0.71	6	10	120
0.61	0.71	6	11	132
0.61	0.71	6	12	144

STATISTICAL ANALYSES AND DESCRIPTION OF MAIN TABLES

Cluster RCT of PriYA-SP intervention

Question: Does the SP training intervention improve *quality* of provider delivery of PrEP services?

Overview: The primary analysis will evaluate effectiveness of the SP clinical training intervention on provider counseling skills and adherence to national guidelines

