- Descriptive statistics, including means, medians, and proportions of data from baseline surveys and SP checklists will be generated including facility size, staffing, HCW age, gender, PrEP training exposure, and years providing HIV prevention services (Table 5). Baseline unannounced SP checklist scores will be presented as mean %. These data will be presented by trial arm in Table 1 to determine whether randomization achieved balance by potential confounding factors. Chi square and ranksum tests will compare differences in categorical and continuous variables by arm. Variables that differ between arms at the $p<0.05$ will be included *a priori* in the regression model.
- An intention-to-treat (ITT) analysis will be used to evaluate whether the SP training intervention resulted in higher mean competency score % at intervention compared to control facilities. The primary outcome will be at the individual level, adjusted for relevant baseline characteristics by arm and baseline evaluation scores. Generalized linear models (GLMM) with a Gaussian distribution and identity link, will be used to the difference in mean score %s between the intervention and standard of care facilities, accounting for facility cluster as a random effect (Table 6). We will consider individual SP as another random effect.

- In sensitivity analyses, we will evaluate the intervention effect on individual components of PrEP competency and communication quality in separate GLMM regression models as well as differences in overall mean % scores between cases, where case is entered as a fixed effect (a covariate).

Data sources: HCW surveys, Facility Surveys, Unannounced SP checklists, Exit Surveys

Figure 1. PrIYA-SP CONSORT diagram

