APPENDIX 2: TABLE SHELLS FOR RCT

* Tables 2-4 suggested for EAC

Table 2. Baseline enrollment summary (N=24 facilities)

Population	# Recruited	# Enrolled	# Withdrawals
Facilities			
Facility Managers			
HCWs			

Table 3. Trial enrollment summary

Facility	# HCW enrolled in study	# HCW trained in study intervention	% trained among enrolled
1			
2			
3			
4			
5			
6			
7			
8			
9			
10			
11			
12			

Table 4. Intervention evaluation progress, Month XXX

Facility	Case 1	Case 2	Case 3	Case 4	Total SP visits
1					
2					
3					
4					
5					
6					
7					
8					
9					
10					
11					
12					
13					
14					
15					
16					
17					
18					
19					
20					
21					
22					
23					
24					
TOTAL VISITS					

Table 5: Baseline characteristics of HIV care facilities and HCW delivering PrEP to AGYW in PrIYA-SP (N=24)

Facility-level characteristics	Overall N or Median, % or IQR	Intervention arm (12 Facilities) N or Median, % or IQR	Control arm (12 Facilities) N or Median, % or IQR
MCH			
FP			
CCC			
Other			
Any adolescent friendly service training			
HCWs trained to prescribe PrEP per facility (all cadres combined)			
Copies of NASCOP PrEP Guidelines (2017) available at this facility (Yes)			
PrEP Services for Adolescents and Young Adults			
Any adolescent-specific PrEP services			
Information about PrEP for AGYW available			
Stockouts of PrEP in last 30 days			
HCW participants (n=XX)			
Female			
Age (years)			
Cadre			
Medical Officer/Doctor			
Clinical Officer/Adherence counselor/Other			
Nurse			
Years of experience providing HIV prevention services to AGYW			
Any prior training in offering HIV prevention (including PrEP) to AGYW			
Baseline provider competency (facility mean score)			
Attitudes about AGYW (facility mean score)			
HIV-related stigma attitudes (facility mean score)			

Table 6. ITT Analysis: Effect of PrIYA-SP intervention on quality of PrEP counseling for AGYW

Outcome	Intervention sites N=12	Control sites N=12	β , 95% CI, p-value	β^* , 95% CI, p-value
Primary HCW quality of PrEP counseling mean score % evaluated by SP using SP checklist				
Sensitivity				
HCW PrEP competency mean score % using SP checklist				
HCW Communication quality mean score % using SP checklist				
Other outcomes				
Self-rated HCW competency				

*Adjusted for pre-specified factors and baseline confounding factors

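### The SAP does not settle whether the rater (individual SP) is in the primary model, and adjusts for case only in a sensitivity analysis; one primary model with both terms should be fixed in advance

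*SAP*

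**What the plan says.** The SAP, under Primary analysis of trial endpoints, plans a Gaussian mixed model with identity link for the endline checklist score and commits it to a facility random effect. The next sentence is "We will consider individual SP as another random effect". It gives no criterion, no time, no decision-maker, and no rule for which result is primary if the two models disagree.

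Case appears in the following bullet, among the sensitivity analyses, "where case is entered as a fixed effect (a covariate").

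No other passage settles the SP question. The SAP's adjustment list, its clustering line (facility only), the Table 6 footnote and the model in Protocol section 8b name neither SP nor case.

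Both factors are part of the design. Protocol section 7 has the SP complete the checklist after each encounter. The shell "Table 4. Intervention evaluation progress, Month XXX" in SAP Appendix 2 counts visits by Cases 1 to 4 for each of 24 facilities. The planned number is six visits per site: "We will plan to conduct 6 visits per site (120 total), which assumes we only have 20 facilities". Neither document says how many SPs there are, or how SPs and cases are allocated to facilities or arms.

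**The concern.** The SP is the measuring instrument. Half of the primary score comes from seven agreement items scored 0 to 3, for a maximum of 21. One category on one item therefore moves the total by 50/21 = 2.4 points. An SP who is one category harsher on two items lowers every score she gives by 4.8 points, about half of the 10-point target difference.

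If the mix of SPs differs by arm, some of that severity enters the arm contrast, and a facility-only model does not count it in the SE. If the mix is the same in both arms, leaving SP and case out costs only precision. Leaving the SP decision open also allows two candidate primary p-values.

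**Working it through.** **Inputs from the SAP.** "Sample sizes of SP encounters to detect a 10-percentage point difference in competency at 80% power"; SD 17.7 ("if PrEP competency is 61% in the control arm using baseline data and standard deviation of 17.7"); k = 0.15; 12 facilities per arm; 6 visits per site.

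**Assumptions, because the documents give no figure.** k read as an intraclass correlation; two-sided α; 8 SPs; SP share of variance r = 5–15%; case SD 0–8 points.

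**1. The plan's own figure.** SAP Table 1 gives 10 clusters per arm at 6 visits.
- Individuals per arm: 2 × (1.96 + 0.84)² × 17.7² / 10² = 49.2.
- With design effect 1 + 5 × 0.15 = 1.75: 49.2 × 1.75 / 6 = 14.3, so 15 clusters.
- With no between-facility variance: 49.2 / 6 + 1 = 9.2, so 10 clusters.

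The stated 10 appears only if k is in effect not applied. That is a separate matter and the present point does not depend on it, but it explains why power below starts under 80%.

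**2. Facility-only SE, all 24 facilities.** V = 17.7² = 313.29.
- SE = √[(2/12) × V × (0.15 + 0.85/6)] = √(52.2 × 0.2917) = 3.90.
- Power at 10 points, noncentral t on 22 df: about 69%. A normal approximation gives 73%, which is too high with 24 clusters.
- If k is instead a coefficient of variation on the point scale, power is about 48%.

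**3. SPs evenly spread over arms.** Modelling SP moves r out of the residual: SE = √[52.2 × (0.15 + (0.85 − r)/6)].
- r = 5%: 3.85. r = 15%: 3.73. The cut from 3.90 is about 1–4%, and 0% if SPs do not differ.
- If cases fall at random over visits with case SD 8, the unadjusted SE is √[(1/6) × (0.15V + (0.85V + 64)/6)] = 4.12, with power 64%. Against 3.73 the cut would be at most 9.5%. Averaging the generalized least squares variance over random designs, which charges for unequal case counts, gives about 8%.
- Power with both terms: about 69–72%.
- If neither factor matters, the SE rises by under 1%.

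**4. SPs tilted 70:30 by arm.** Four SPs make 70% of the visits in one arm and 30% in the other; the other four do the reverse. Each SP's share is 0.175 in one arm and 0.075 in the other.
- Squared differences: 8 × 0.10² = 0.080.
- Chance variation over 72 visits per arm: 8 × (0.175 × 0.825 + 0.075 × 0.925)/72 = 0.024.
- True variance = 52.2 × (0.15 + (0.85 − r)/6) + 0.104 × r × V.
- r = 5%: 14.8 + 1.6 = 16.4, SE 4.05. r = 15%: 13.9 + 4.9 = 18.8, SE 4.34.
- The facility-only model still reports about 3.90. Type I error = 2 × P(T₂₂ > 2.074 × 3.90 / true SE), about 5.8% and 7.6%.

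**5. Simulation with other assumed SP numbers (2 or 6 SPs, share 2–10%).**
- Facility-only type I error is 4.6–5.5% when SPs are balanced or randomly assigned.
- It is 5.2–12.1% under a 70:30 tilt.
- Taking the smaller p of the two models, with 6 SPs, gives 5.2–5.8% when balanced or random.
- Under the tilt with SP share 10% the smaller p gives 9.0%, against 5.8% when SP is always modelled (500 runs, Monte Carlo error about 1 point).

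**The case against.** Leaving a prognostic covariate out of the primary model is a legitimate choice when it is made in advance, and that is what the SAP does with case. A reader might infer that case is also open to later choice. It is not, and that part of the objection stands in full.

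A reader might also infer that the primary test is invalid. The documents do not support this. The Methods paragraph of the SAP summary has the SP mystery shoppers visiting both intervention and control facilities, which describes one pool of raters crossing the arms. Protocol section 6b trains actors for both assessment and training, and section 6d gives the training to intervention staff only. From this one might suppose that different SPs were sent to each arm to avoid recognition, with much larger error rates. Nothing in the documents says so, and the SAP summary points the other way. Still, visiting both arms does not mean equal shares, and no passage fixes the shares.

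Six visits cannot be equal over four cases within a site, but this does not threaten the arm contrast. Twelve sites give 72 visits per arm, or 18 per case; ten sites give 60, or 15 per case. Balance by arm is achievable, and Table 4 allows it to be monitored.

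Finally, the size of the harm rests on assumed SP numbers, variance shares and tilt. That is true, and it is why the figures are ranges.

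**Conclusion.** The point holds in a limited form. The SP term in the primary model is undecided and should be decided before unblinded analysis. Case is omitted by plan, and adding it is an inexpensive improvement, not the repair of an error.

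The facility-only test is sound if SPs and cases are balanced or randomly spread over arms. The exposure is about 6–8% type I error under an assumed 70:30 tilt with 8 SPs and an SP share of 5–15%. With even spread, the benefit is an SE lower by about 0–8%. Even with both terms, power at 10 points stays below 80% when k is read as an intraclass correlation.

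The documents do not show whether the SP decision came before endline data. The SAP is dated September 2021 and gives a timeframe ending August 2020; the Protocol gives August 2022. This is a reason to record the decision, not evidence that it was made after the data were seen.

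**What to change.** Before unblinded analysis, replace the sentence on SP with one stated primary model: score on arm, facility size stratum, baseline score and case (four-level fixed effect), with random facility and random SP. SP and case stay in whatever their estimated size.

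Add the following:
- **Fallback.** If the SP variance is estimated at zero or the fit fails, use a model named in advance, for example SP as fixed effects, or facility plus case only.
- **Aliasing.** If each SP plays only one case, the two effects cannot be separated; keep a single SP term.
- **Sensitivity.** Report the model without SP and case as the sensitivity analysis.
- **Description.** Tabulate visits by SP and by case within arm. Confirm that an SP identifier is held for every checklist; the documents imply this but do not list the field.
- **Scheduling.** If endline visits are not complete, balance SPs and cases by arm. If they are complete, this step lapses and the model carries the adjustment.

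The cost is a few SAP sentences, 3 degrees of freedom and one variance component, with no new data if the SP identifier is already recorded. A visit schedule, if still possible, is an added operational task.

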5. APPENDICES

APPENDIX 1: DATA SOURCES

Data source	Description	Timing of data collection	Analysis purpose
Unannounced SP checklist	Standardized SP checklists to evaluate the HCW encounter with the SP actor at baseline and endline unannounced visits	Baseline and end of study	Primary outcome End of study scores will be compared between RCT arms; Baseline scores used as an adjustment variable
Facility Survey	Anonymous survey will be administered to a health facility manager at baseline to capture facility characteristics	Baseline	Assess adequacy of randomization; Provide data for potential adjustment of ITT analysis
HCW surveys	Pre/post surveys to assess knowledge of and self-rated competency in provision of PrEP to AGYW	Baseline and end of study	Assess change in knowledge/attitudes between baseline and end of study, all sites Compare end of study scores between trial arms
SP training checklist	Standardized SP checklists to evaluate quality of the simulated visit with HCWs in the intervention training	Immediately after each SP encounter among trial participants	Secondary outcome Change in mean competency % among intervention participants between the first and last session

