Study staff will take strict measures to maintain confidentiality for all participants. No names will be recorded on data collection forms. HCW participants will be assigned unique study identification (ID) numbers. Participants will be assigned a non-identifiable study code upon enrollment. Study analysts will receive only coded data. The links to participant identifiers will be retained in a password-protected file on an encrypted computer. Data collected will be kept confidential and access restricted to study staff. All video-recordings of the SP encounters will be kept in an encrypted cloud server. Video data are potentially identifiable. Only

videos of HCWs who have signed release waivers will be stored after the two-day training. All other data will be kept in password-protected databases, in a locked study office, accessible only to study personnel.

11c. Risks and Benefits

Physical risks: There are no medical interventions associated with the study, therefore we anticipate no risk of serious physical harm to participating HCWs.

Psychosocial or other risks: Other potential study risks to the HCW participants include breach of confidentiality, emotional distress associated with the sensitive nature of HIV counseling for AGYW, and stress associated with group critique/feedback of videotaped training encounters.

Procedures to minimize psychological risks: All participants will be assured that their participation is voluntary and that they may withdraw from the study at any time. Trained facilitators will oversee debriefing sessions with HCWs. For HCW training attendees, each clinical training intervention will begin with a session on professional standards, expectations, and confidentiality, building an atmosphere of peer-support and collaboration. All HCW participants will agree to not share individual performance information from the SP trainings outside of the learning group.

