Primary outcome: Provider competency score using the endline unannounced SP checklist, expressed as a mean %, at the individual level. Each provider will receive a total score (% correct) from the checklist, rescaled to be out of 100.

Computing the total score per provider:

- The unannounced SP checklist contains 12 questions on adherence to PrEP guidelines with binary (done/not done) response options and 7 items on communication quality with 4 scaled response options (strongly agree to strongly disagree). Higher total scores represent higher competency.
- Each binary response option will be assigned 1 for 'done' and 0 for 'not done' for a total possible sub-score of 12.
- Communication items number #4, and 6-10 will be scored 3=strongly agree, 2=agree, 1=disagree, 0=strongly disagree. Question #5 is reverse coded (it is a negative question) as 3=strongly disagree, 2=disagree, 1=agree, 0=strongly agree, for total possible sub-score of 21.
- Each domain score will be converted a percentage of points possible. Total scores will be computed by adding the converted percentages and dividing by 2 (the number of domains), so that each domain is weighted equally.

Exposure: 12 Facilities that received the SP training intervention compared to 12 facilities without the SP intervention.

Adjustment variables: Pre-specified facility size/level, any baseline factors that differ between arms at $p<0.05$ level in addition to the primary exposure (intervention v. control) and stratification variables.

Clustering: Individuals within facilities

Data sources: HCW surveys, Facility survey, unannounced SP actor checklists

Primary analysis of trial endpoints: Primary analysis will be intention-to-treat (ITT).

[figure not shown]
A CONSORT diagram will be used to show the number of facilities and HCWs by arm during the trial, numbers excluded, and reasons for exclusion (Figure 1).

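### The between-arm comparison of HCW survey scores does not prespecify adjustment for each HCW's own baseline survey score, so precision may be given up on an outcome of low rank

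*SAP*

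**What the plan says.** SAP Appendix 1 describes the HCW surveys as "Pre/post surveys to assess knowledge of and self-rated competency in provision of PrEP to AGYW", timed at baseline and end of study. It gives them two uses: "Assess change in knowledge/attitudes between baseline and end of study, all sites" and "Compare end of study scores between trial arms". Neither names a baseline covariate.

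The SP checklist row of that table, which serves the primary outcome, does name one: "Baseline scores used as an adjustment variable". The SAP's analysis text agrees, again for the primary outcome: "The primary outcome will be at the individual level, adjusted for relevant baseline characteristics by arm and baseline evaluation scores".

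Table 6 (SAP Appendix 2) places self-rated HCW competency in its last group, below the primary and sensitivity rows. It has columns for an unadjusted and an adjusted coefficient. The footnote to the adjusted column reads "Adjusted for pre-specified factors and baseline confounding factors". The SAP's adjustment variables are defined as "Pre-specified facility size/level, any baseline factors that differ between arms at $p<0.05$ level", together with the arm indicator and the stratification variables.

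On linkage, Protocol section 11b says "HCW participants will be assigned unique study identification (ID) numbers".

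**The concern.** Two measures are taken before and after the intervention. For the SP checklist the SAP commits to baseline adjustment. For the HCW survey it is silent, and the one route by which a baseline survey score is assured entry is a significance test of baseline balance. That test responds to the size of a chance difference. It does not show how well the baseline score predicts the end-of-study score, and prediction is what determines the gain in precision. It also leaves the covariate set unknown until the data are seen. Table 5 lists the attitude and stigma scores as facility means, so a score that entered by this route might be a facility mean and not the HCW's own value.

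At stake are the width of the interval for the survey comparison and its exposure to chance baseline differences, with only 12 facilities per arm. A lesser matter is that the all-sites change from baseline has no stated arm contrast and no table shell. Shown without a split by arm, it would mix trained HCWs, untrained HCWs and any secular trend.

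**Working it through.** **No figure to reproduce.** The documents give no sample size, SD, target difference, power or baseline to end-of-study correlation for the survey. The sample-size tables in both documents concern SP encounters.

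**Inputs**
- HCWs: about 10 per site, 240 in total (Protocol 5d), hence 120 per arm in 12 facilities.
- Clustering coefficient: 0.15, stated for the primary outcome (SAP Table 1). It is used here as an intraclass correlation (ICC), which is an assumption for the survey.
- Correlation r between an HCW's baseline and end-of-study scores: assumed 0.3, 0.5 or 0.7, and taken as equal at HCW and facility level.
- Every HCW has both surveys (assumed).
- Two-sided α of 0.05 and 80% power, so the multiplier is 1.96 + 0.84 = 2.80.

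**Formulas**
- Variance of the adjusted contrast relative to end-of-study scores alone: 1 − r².
- Relative confidence interval width: √(1 − r²).
- Design effect: 1 + (10 − 1) × 0.15 = 2.35.
- Detectable difference in SD units: 2.80 × √(2 × 2.35 × (1 − r²) / 120).

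| r | 1 − r² | Variance cut | CI width factor | CI narrower by | Detectable difference (SD) |
|---|---|---|---|---|---|
| no adjustment | 1 | – | 1 | – | 0.55 |
| 0.3 | 0.91 | 9% | 0.954 | 4.6% | 0.53 |
| 0.5 | 0.75 | 25% | 0.866 | 13.4% | 0.48 |
| 0.7 | 0.51 | 49% | 0.714 | 28.6% | 0.40 |

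At an assumed ICC of 0.05, the detectable difference goes from 0.44 SD to 0.42, 0.38 or 0.31 SD. For an illustrative difference of 0.5 SD at ICC 0.15, power is 71% without the covariate and 75%, 83% or 94% with it.

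**Why no equivalent number of HCWs is given.** The factor 1/(1 − r²) applies to independent subjects, but here the facilities are fixed at 24. In units of the outcome variance, a facility mean at ICC 0.15 has variance 0.85/10 + 0.15 = 0.235. Doubling to 20 HCWs gives 0.85/20 + 0.15 = 0.1925, a cut of only 18%. The r = 0.7 target is 0.51 × 0.235 = 0.120. That lies below the floor of 0.15, so no number of HCWs per site reaches it.

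**Dependence on control-arm baselines.** In simple ANCOVA form the adjusted difference is (ȳ₁ − ȳ₀) − b(x̄₁ − x̄₀), where x is the baseline score. If no control HCW had a baseline survey and each was given the overall mean, x̄₁ and x̄₀ would be equal. The adjusted difference would then be the unadjusted one, with nothing gained.

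The documents differ on this premise:
- Protocol section 7 times the HCW surveys around the SP training, and section 6d limits control HCWs to the unannounced SP assessments.
- The SAP refers to change at all sites, presents baseline survey data by arm, and gives Table 5 a control column for the attitude scores.

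**The case against.** The strongest case for leaving the SAP as it is has five parts.

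1. *The comparison is valid as planned.* A reader might infer that comparing end-of-study scores alone biases the survey result. It does not, because the arms are randomised. This stands, and it limits the point to efficiency and chance imbalance.
2. *It is not wholly unadjusted.* A reader might infer that no adjustment is planned. Table 6 has an adjusted column for self-rated competency. Its footnote also serves the primary row, where baseline-score adjustment is prespecified, so prespecified factors cannot mean facility size alone throughout the table. Whether they include the survey's own baseline is not said. The documents therefore support a finding that the covariate is not assured; they do not show that it is excluded.
3. *Pooling is not stated.* A reader might take the all-sites change to be a reported figure that combines the arms. The SAP says where change is assessed, not that arms are combined, and no table shell reports it. This stands; the phrase is ambiguous.
4. *The control-arm baseline may not exist.* The protocol wording leaves this open, and withdrawal or relocation of HCWs (Protocol 5e) would reduce pairing even if it does. This stands as a condition on the gain. The SAP is the later document and plans for baseline survey data in both arms.
5. *The outcome ranks low.* It is neither the primary outcome nor the named secondary, and nothing was sized on it. This stands and sets the severity.

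None of this explains why the checklist row names its baseline score as a covariate and the survey row does not.

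**Conclusion.** The point holds as a low-severity matter of efficiency. The SAP plans to collect a baseline survey score but does not commit to using it in the between-arm comparison, and its adjustment rule assures entry only after a significant imbalance.

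The size of the loss cannot be fixed from the documents. At assumed correlations of 0.3, 0.5 and 0.7, the unused gain is about 9%, 25% and 49% of the variance, or 5%, 13% and 29% of the interval width. These figures need equal correlation at HCW and facility level and full pairing. Incomplete pairing lowers them, and absent control-arm baselines would remove the gain. No conclusion about the primary outcome depends on this.

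**What to change.** 1. **Reconcile first.** Bring Protocol sections 6d and 7 into line with SAP Appendix 1 on whether, and when, control-arm HCWs complete the baseline survey.
2. **Prespecify the model.** For self-rated HCW competency in Table 6, and for any other survey score compared between arms, regress the end-of-study score on arm, facility-size stratum and the same HCW's baseline survey score, with a facility random effect. Replace a missing baseline covariate with the overall mean. Say so in the survey row of Appendix 1 and in the Table 6 footnote.
3. **Show change by arm.** Present the all-sites baseline to end-of-study change as means by arm.

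The cost is one covariate in a model already planned and a few sentences in the SAP. If the SAP's plan for baseline surveys in both arms is confirmed, no new data are needed. If it is not, item 2 would bring no gain.
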